### **3.2. Dose Reductions and Discontinuations**

Subjects are allowed one dose reduction in the study, based on TEAE severity grade (Grade 1 or 2), system organ class (non-skin or non-eye vs skin or eye) and duration of TEAE resolution (< 7 days or  $\geq$  7 days). Subjects who experience TEAE with severity Grade 3 or higher will result in permanent treatment discontinuation. Please see protocol section 6.6 for more details.

### **3.3. Study Procedures**

For detail on all the assessments, please see the Schedule of Events (SOE) in the Appendix A.

### **3.4. Sample Size Consideration**

With 10 evaluable subjects in the treated group and 10 evaluable subjects in the control group, there is 84% power to detect a difference of 20% in MRI-PDFF between any dose of FT-4101 treated group and the pooled placebo subjects in cohorts A and B, assuming a standard deviation of 14% using a one-sided Wilcoxon-Mann-Whitney test with an alpha of 0.05.

The total sample size will be 30 subjects, 15 subjects per cohort randomized 2:1 to receive FT-4101 or placebo.

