	
To assess the PD effect of FT-4101 after administration of multiple doses in overweight/obese subjects with NASH by assessment of circulating metabolic parameters, such as but not limited to:
 

• Fasting Lipids

○ Total cholesterol

○ Low-density Lipoprotein cholesterol (LDL-c) direct

○ High-density Lipoprotein cholesterol (HDL-c)

○ Non-HDL cholesterol (non-HDL-c)

○ Triglycerides (TG)

○ Free fatty acids (FFA)

• Glycemic parameters

○ Fasting plasma glucose (FPG)

○ Fasting insulin

○ HOMA-IR

○ HbA1c

• Adiponectin (total and high molecular weight)

• FGF-21

• Malonyl carnitine

	
To assess the PD effect of FT-4101 after administration of multiple doses in overweight/obese subjects with NASH by assessing steatosis (CAP) and liver stiffness (LSM) determined by FibroScan® at 12 weeks.
 
To assess the effect of FT-4101 after administration of multiple doses in overweight/obese subjects with NASH on imaging parameters assessed by MRI-PDFF:
 

• Liver Volume (L)

• Liver Fat Volume Index (L)

Phase of Development	Phase 1/2
Number of Study Sites	Up to 3 sites

Study Population	Overweight/Obese subjects with NASH
Number of Subjects	At least 30 subjects, divided in 2 cohorts with at least 15 subjects per cohort. Drop-outs may be replaced in order to enroll sufficient subjects into the study, only after discussion with Sponsor and Investigator.

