	30. Any other condition which, in the opinion of the investigator would impede competence or compliance or possibly hinder completion of the study.
Sample Size	A sample size of 15 subjects per cohort is empirically determined to assess the safety of the dose and characterize the PK. The total number of subjects will be approximately 30; 20 treated with FT-4101 and 10 with placebo. With 10 evaluable subjects in the treated group and 10 evaluable subjects in the control group, there is 84% power to detect a difference of 20% between the high dose treated group (cohort B) and the pooled placebo subjects from cohorts A and B in MRI-PDFF, assuming a standard deviation of 14% using a one-sided Wilcoxon-Mann-Whitney test with an alpha of 0.05.
Statistical Methods	Data analyses will follow a statistical analysis plan (SAP). The overall safety profile of FT-4101 will be assessed as the percentage of participants experiencing TEAE, serious TEAEs, TEAEs leading to premature study drug discontinuation, and treatment-emergent clinically significant laboratory abnormalities. Safety analysis will involve examination of the descriptive statistics and individual subject listings for any effects of study treatment on clinical tolerability and safety. Efficacy, PK and PD assessments for all dose groups will be analysed using descriptive methods; figures (bar charts or line plots) may also be generated to visualize the data. The primary preliminary efficacy analysis of the reduction (absolute and relative) of % liver fat on magnetic resonance imaging-estimated proton density fat fraction (MRI-PDFF) at 12 weeks will be analyzed using a Wilcoxon rank-sum test. The test will be one-sided and use a significance level of 0.05. Subjects in each dose group will be tested against the pooled placebo subjects from each cohort. If more than one dose of FT-4101 is evaluated, control of the alpha level will be accomplished using Holm's Sequential Bonferroni procedure [Holm 1979] to test each FT-4101 dose against the pooled placebo subjects. The secondary preliminary efficacy analysis of the reduction (absolute and relative) of % liver fat on magnetic resonance imaging-estimated proton density fat fraction (MRI-PDFF) at 6 weeks will be analyzed similarly. The secondary preliminary efficacy analysis of the proportion of subjects with $\geq 30\%$ relative reduction in liver fat at week 12 assessed by MRI-PDFF will be analyzed using a Fisher's exact test.

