#### 12.5.1.1 Liver Fat Assessed by MRI-PDFF at 12 weeks

The observed values and the change (absolute) from baseline and the percent change from baseline of liver fat estimated from MRI-PDFF will be analyzed descriptively by treatment group and visit.

Change at Week 12 (absolute and relative) in percentage of liver fat as assessed by MRI-PDFF will be analyzed by a Wilcoxon rank-sum test. The test will be one-sided and use a significance level of 0.05. Subjects in each dose group will be tested against the pooled placebo subjects from each cohort.

If more than one dose of FT-4101 is evaluated, control of the alpha level will be accomplished using Holm's Sequential Bonferroni procedure [Holm 1979] to test each FT-4101 dose against the pooled placebo subjects.

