## 12.8 Determination of Sample Size

With 10 evaluable subjects in the treated group and 10 evaluable subjects in the control group, there is 84% power to detect a difference of 20% between the high dose treated group and the pooled placebo subjects in cohorts A and B in MRI-PDFF, assuming a standard deviation of 14% using a one-sided Wilcoxon-Mann-Whitney test with an alpha of 0.05.

The total sample size will be 30 subjects, 15 subjects per cohort randomized 2:1 to receive FT-4101 or placebo.

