### **6.1.2. Hypothesis Testing and Multiplicity Adjustment**

The primary preliminary efficacy endpoint will be tested using a one-sided test at an alpha level of 0.05. The null hypothesis and alternative hypothesis are presented below.

$$H_0: \text{Diff} \geq 0$$

$$H_a: \text{Diff} < 0$$

Where Diff is the mean difference: FT-4101 minus Placebo.

If more than one dose of FT-4101 is evaluated, control of the alpha level will be accomplished using Holm's Sequential Bonferroni procedure to test each FT-4101 dose against the pooled placebo subjects. There will be two comparisons.

The p-values of the multiple comparisons will be ordered from smallest to largest. The corrected p-value from each comparison, starting from the smallest original p-value, will be calculated based on the following formula:

$$p_{\text{Bonferroni},i|C} = (C - i + 1) * p$$

where the number of comparisons is  $C$ , index  $i$ , ranges from 1 to  $C$ , and the original p-value that is to be corrected,  $p$ . Corrected p-values less than 0.05 will be considered statistically significant.

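### The stated 84% power is per comparison before Holm; the plan decides by Holm, which lowers power for a given dose by about 3 to 9 points, method held fixed

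*SAP*

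**What the plan says.** There are three power statements. Protocol 2.0: "there is 84% power to detect a difference of 20% between the high dose treated group (cohort B) and the pooled placebo" subjects. Protocol 12.8: "there is 84% power to detect a difference of 20% between the high dose treated group and the pooled placebo subjects". SAP 3.4: "there is 84% power to detect a difference of 20% in MRI-PDFF between any dose of FT-4101 treated group and the pooled placebo" subjects. All three assume a standard deviation of 14%, a one-sided Wilcoxon-Mann-Whitney test at alpha 0.05, and 10 evaluable subjects in each of the two groups. None mentions Holm, names the power formula, or states a distribution. The protocol applies the figure to the high dose and the SAP to either dose.

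The decision rule is elsewhere. Protocol 12.5.1.1: "If more than one dose of FT-4101 is evaluated, control of the alpha level will be accomplished using" Holm's procedure. SAP 6.1.2 uses Holm "to test each FT-4101 dose against the pooled placebo subjects. There will be two comparisons", multiplies the i-th smallest p-value by (C − i + 1), and states: "Corrected p-values less than 0.05 will be considered statistically significant". SAP 6.10.1.1 applies this to the Week 12 liver-fat test.

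On numbers, SAP 3.4 says "The total sample size will be 30 subjects, 15 subjects per cohort randomized 2:1 to receive FT-4101 or placebo", and Protocol 2.0 says "At least 30 subjects, divided in 2 cohorts with at least 15 subjects per cohort".

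**The concern.** The power is stated at one-sided 0.05, but when both doses are tested a raw p-value just under 0.05 cannot produce the first rejection. With two comparisons the smaller p-value is doubled before it is compared with 0.05. The calculation and the decision rule therefore use different thresholds, and the power text does not say so.

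This is the only quantitative justification given for the liver-fat comparison. It bears mainly on a null result: someone judging how likely the study was to miss a real 20% effect would take 16% from the stated 84%, and that is not the miss rate under the rule the plan applies.

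**Working it through.** **Inputs (SAP 3.4, Protocol 12.8).** Difference 20%, SD 14%, 10 v 10 evaluable, one-sided alpha 0.05. Standardised difference d = 20/14 = 1.429.

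**Step 1. Reproduce 84%.** For normal data, P(X<Y) = Φ(d/√2) = 0.8438. Noether's power, with N = 20 and c = 0.5, is

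Φ( √(12·c·(1−c)·N) · (P − 0.5) − z ).

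Here √(12 × 0.25 × 20) = √60 = 7.746, and 7.746 × 0.3438 = 2.663. With z = 1.645: Φ(1.018) = 84.6% (83.9% if P is rounded to 0.84). The stated figure is reproduced. At one-sided 0.05 other standard methods do not give it: t-test 92.3%, t-test with efficiency 3/π 91.1%, exact rank-sum on normal data 89.8%. Noether is an inference from this match.

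**Step 2. Threshold set by Holm.** C = 2. Smaller p-value: (2 − 1 + 1)·p = 2p < 0.05, so p < 0.025. Larger p-value: multiplier 1, so p < 0.05. I take the procedure as sequential, as its name says: the second comparison counts only after the first is rejected.

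**Step 3. Noether under Holm.**
- Other dose not rejected: z = 1.960, so Φ(2.663 − 1.960) = Φ(0.703) = 75.9% (75.0% with P rounded to 0.84).
- Both doses have the 20% effect: two normal statistics, each with mean 2.663, correlation 0.5 from the shared placebo group, simulated 300,000 times. Given dose 81.4%; at least one dose 88.5%.

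**Step 4. The planned test under Holm.** Exact rank-sum, normal data, shared placebo, 10 per group, simulated. The critical values have attained size 0.0446 and 0.0216.

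| Power for a given dose | Noether | Exact rank-sum |
|---|---|---|
| One comparison at 0.05, before Holm | 84.6% | 89.8% |
| Holm, other dose inert | 75.9% | about 81.7% |
| Holm, other dose has half the effect | not computed | 82.6% |
| Holm, both doses have the full effect | 81.4% | 87.1% |

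With equal effects, the exact test rejects for at least one dose with probability 92.5%.

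**Step 5. Size of the change, method held fixed.** Noether: 84.6 − 75.9 = 8.7 points at most, 84.6 − 81.4 = 3.2 at least. Exact: 89.8 − 81.7 = 8.1 and 89.8 − 87.1 = 2.7. The chance of missing the effect for a given dose goes from 15.4% to between 18.6% and 24.1% by Noether, and from 10.2% to between 12.9% and 18.3% by the exact test.

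**Sensitivity, on an assumed loss.** The documents give no loss rate. If 9 v 9 were evaluable, first-step power at 0.025 would be 71.4% (Noether) or 75.5% (exact); at 8 v 8, 66.3% or 73.3%.

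**The case against.** The best reply is that 84% is about right for the plan as it will be run. On normal data the exact rank-sum test with full Holm gives about 82% to 87% for a given dose, a range that contains 84%; the asymptotic test without continuity correction gives 84.1% (other dose inert) to 89.1% (equal effects). This stands. It follows that a reader who infers that the study has only 76% power goes further than the documents allow. That figure comes from a conservative formula the documents do not name, and it is the floor for one dose when the other is not rejected.

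A reader might also infer that the arithmetic is wrong or the meaning of 84% hidden. Neither is supported. The figure is correct for the single test described, the text gives alpha 0.05 and one treated group against pooled placebo, and Holm is set out openly in both documents, including the row after the power statement in the Protocol 2.0 synopsis.

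The method cannot be settled from the text. Two methods give about 84% at 0.025 (asymptotic rank-sum 84.1%; t-test with efficiency 3/π 83.7%). If one of them had been used, the stated alpha of 0.05 would be wrong. That is a reason to name the method, not to leave the text alone.

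Two further points limit the weight. Protocol 2.0 says 15 per cohort was chosen empirically for safety and PK, and Protocol 6.3 calls the study exploratory, so power did not set n. And although 30 randomised at 2:1 yields exactly the 10 v 10 needed, the power text is conditional on evaluable subjects and the protocol allows discretionary replacement. A claim that losses will erode power would need a rate the documents do not give.

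What the reply does not remove is the mismatch: the stated alpha is not the one that decides a first rejection, and by either method the like-for-like power under Holm is lower.

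**Conclusion.** The point holds as a matter of labelling and completeness. The 84% is correct for one dose against pooled placebo at one-sided 0.05 with 10 v 10 evaluable, but the primary test is decided by Holm, where the smaller raw p-value must be below 0.025. By Noether, power for a given dose under Holm is about 76% to 81%, against 84.6% before Holm. By the exact planned test it is about 82% to 87%, against 89.8%. The lower end applies when the other dose is inert, the upper end when both doses have the full 20% effect.

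This rests on normal data with a common SD of 14%, all 10 v 10 evaluable at Week 12, both doses tested, and (for the first pair of figures) Noether being the method used. If only one dose is evaluated, Holm does not apply and alpha stays at 0.05. The finding does not show that the study is too small or that the analysis should change.

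**What to change.** Keep n=30 and the analysis as planned. In Protocol 2.0, Protocol 12.8 and SAP 3.4:

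1. Label 84% as per comparison, one-sided 0.05, before Holm, with 10 v 10 evaluable at Week 12.
2. State the power method and the assumed distribution.
3. Beside it, give the power for a given dose under Holm by that same method, as a range from the other dose being inert to both doses having equal effects. If the method is Noether, that is about 76% to 81%, with about 89% for at least one dose when both work. Do not present 76% as the study's overall power.

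Optional: use the same dose wording in both documents (high dose or either dose), which changes no number. If a sensitivity to lost scans is added, label the loss as an assumption.

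The cost is a few sentences of wording and a less favourable figure beside the present one. Sample size, conduct and analysis are unaffected.

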## **4. ANALYSIS SETS**

The number of subjects and percentage of subjects in each analysis set will be summarized. A memo will be finalized prior to database lock to adjudicate each subject's membership in each analysis set based on the following pre-specified definitions.

### **4.1. Randomized Analysis Set**

The Randomized analysis set will include all randomized subjects. The Randomized analysis set will be used for summary of subject disposition, demographic, and baseline characteristics.

#### **4.2. Safety Analysis Set**

The Safety analysis set will include all randomized subjects who received IP (FT-4101 or Placebo) or deuterated water. Subjects who took deuterated water and were not randomized will be excluded. The Safety analysis set will be used for safety summaries.

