### Run-in Period:

#### *Outpatient Visit on C1/D-14 (Start of first deuterated water administration period):*

Subjects will check into the clinic in the morning of C1/D-14 in fasting conditions. Sebum and blood for PD assessments will be collected prior to the administration of deuterated water. Subjects will be provided with the first administration of 50 mL deuterated water under in-house surveillance for subjects' safety. Subjects will be provided with a supply of deuterated water and will get instructions on how to continue the administration of the deuterated water at home. Subjects will be asked to record their deuterated water intake in a subject diary for compliance reason. Subjects will be contacted/called daily to ensure compliance during the water labeling period. Subjects will be counseled to maintain their normal diet and exercise regimen.

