### 12.2 Analysis Sets

#### 12.2.1 Safety Set

The Safety set will include all subjects who received IP (FT-4101 or Placebo) or deuterated water. The Safety set will be used for demographic, baseline characteristics and safety summaries.

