## **12.6 Analysis and Endpoints**

### **12.6.1 Analysis of Primary Safety and Tolerability Endpoints**

To assess safety and tolerability of FT-4101 after administration of multiple doses in overweight/obese subjects with NASH by:

- Incidence of treatment-emergent adverse events (TEAEs)
- Incidence of clinical lab abnormalities
- Incidence and severity of clinical findings on physical examination

- Change from baseline in vital signs (blood pressure [BP], heart rate [HR], respiratory rate, and temperature])
- Change from baseline in 12-lead electrocardiogram (ECG) parameters

Safety and tolerability of the study drugs will be assessed by collection and review of adverse events, tolerability, laboratory parameters, physical examination, vital signs, and ECG parameters throughout the duration of the study. Safety analysis will involve examination of the descriptive statistics and individual subject listings for any effects of study treatment on clinical tolerability and safety.

AEs will be summarized using the safety set.

All AEs will be coded using MedDRA. Data will be summarized using preferred term and primary system organ class.

Adverse event summaries will include the overall incidence (by system organ class and preferred term), events by maximum intensity, event by relationship to study treatment, events leading to discontinuation of study drug, and serious adverse events. Physical exam, vital signs, ECG, and laboratory parameters (hematology, chemistry, and urinalysis) will be summarized descriptively by treatment group.

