### **6.11.1. Analysis of Primary Safety and Tolerability Endpoints**

#### **6.11.1.1. Adverse Events**

The latest version of the Medical Dictionary for Regulatory Activities (MedDRA version 22.0) will be used to code adverse events (and medical history). TEAEs will be summarized by treatment group. TEAE is defined as an adverse event with an onset that occurs after receiving the first dose of the study drug (AE start date  $\geq$  first dose date) and within 30 days after receiving the last dose of the study drug (AE start date – last dose date  $\leq$  30). TEAEs will be tabulated including the following categories:

- TEAEs by System Organ Class and Preferred Term.
- Drug-related TEAEs by System Organ Class and Preferred Term. Related includes: Definitely Related, Possibly Related, or Probably Related; Unrelated includes: Not Related or Unlikely to be related. If drug relationship is missing, event will be considered related to the study drug.
- TEAEs Leading to Discontinuation of Study Drug by System Organ Class and Preferred Term.
- Serious TEAEs by System Organ Class and Preferred Term.
- Drug-related Serious TEAEs by System Organ Class and Preferred Term.
- Serious TEAEs Leading to Discontinuation of Study Drug by System Organ Class and Preferred Term.
- Severity of TEAEs by System Organ Class and Preferred Term. Severity of TEAEs will be presented using National Cancer Intuitive Common Toxicity Criteria for Adverse Events (CTCAE) grade. Subjects with same AE more than once will have the maximum CTCAE grade counted within system organ class and preferred term.

In each AE summary table above, subjects with same AE more than once will be counted only once within the same system organ class and preferred term.

An overall summary TEAE table will be also provided to present number and percentage of subjects who had any TEAE, drug-related TEAE, CTCAE grade 3 or higher AE, CTCAE grade 3 or higher drug-related TEAE, serious TEAE, drug-related serious TEAE, TEAE leading to drug discontinuation, TEAE leading to on-study death. On-study death is defined as death as the death that occurs between the first date of study drug and within 30 days after the last date of study drug.

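### Counting deuterated water as exposure makes the SAP Safety set match the Randomized set, so any randomized but never-dosed subject would stay in the TEAE denominators

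*SAP*

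**What the plan says.** **The set.** SAP 4.2 defines the Safety set as "all randomized subjects who received IP (FT-4101 or Placebo) or deuterated water" and adds: "Subjects who took deuterated water and were not randomized will be excluded". On its use, it says: "The Safety analysis set will be used for safety summaries". Protocol 12.6.1 agrees: "AEs will be summarized using the safety set". For the comparison set, SAP 4.1 says: "The Randomized analysis set will include all randomized subjects".

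**The protocol version.** Protocol 12.2.1 (Safety Set) also treats water as exposure, but sets no randomization condition: "The Safety set will include all subjects who received IP (FT-4101 or Placebo) or deuterated water". SAP section 7, which is reserved for changes from the protocol, names only a supportive t-test.

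**The timing.** Protocol 6.2 places the first water at the C1/D-14 visit: "Subjects will be provided with the first administration of 50 mL deuterated water under in-house surveillance". Randomization follows at C1/D-1 and the first IP dose at C1/D1.

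**The event.** SAP 6.11.1.1 states: "TEAE is defined as an adverse event with an onset that occurs after receiving the first dose of the study drug". The window closes 30 days after the last dose. The rules for incomplete onset dates in SAP 6.1.5.1 refer to the date of the first randomized dose, so the study drug meant here is IP, not water.

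**The concern.** A safety set usually separates subjects who were exposed to the study drug from those who were only randomized. Here the water clause removes that separation. TEAE incidence is a primary endpoint and the planned groups are small, so one person who cannot enter the numerator but is counted in the denominator visibly lowers the percentage.

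Two reporting points go with it. Adverse events between first water and first IP dose are collected but have no planned frequency table. The SAP also narrows the protocol's Safety set without recording the change in section 7.

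**Working it through.** The plan states no TEAE rate, so there is none to reproduce. The check is set logic on the visit schedule, followed by a simple ratio.

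**Step 1: membership.**
- SAP Safety set = randomized AND (IP OR water).
- Water starts at C1/D-14 (protocol 6.2) and runs to C1/D-8 (protocol 8.5.1). Randomization is at C1/D-1, after this whole first water period.
- For anyone randomized on schedule the water condition is already met, so the definition reduces to being randomized. That is the Randomized set of SAP 4.1. With the planned numbers, both sets hold 30.

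**Step 2: who can have a TEAE.**
- Onset must be on or after the first IP dose, so a never-dosed subject contributes 0 to the numerator and 1 to the denominator.
- Such a subject is possible. On C1/D1, after randomization, clinical assessments precede dosing (protocol 6.2), and a negative serum pregnancy result must be in hand before dosing (protocol 9.1.12).
- SAP 6.1.1 leaves the choice of denominator open between subjects and records and gives no rule for never-dosed subjects.
- In the TEAE tables the water clause brings in no run-in event. Its only possible effect there is to add never-dosed subjects to the denominators.

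**Step 3: size.**
- Group sizes: 15 per cohort at 2:1 gives 15 × 2/3 = 10 active and 15 × 1/3 = 5 placebo. Two cohorts give 10 per FT-4101 dose and 5 + 5 = 10 placebo if pooled. SAP 6.10 states pooling for efficacy and pharmacodynamics; I assume the same for TEAEs.
- Let n be the group size, m the number randomized but never dosed, and k the number with a TEAE. Reported rate = k/n. Rate in dosed subjects = k/(n − m). Ratio of reported to dosed-subject rate = (n − m)/n.
- The documents give no value for m. I assume 0 to 2, with n = 10:

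| m | ratio | k = 4: reported / dosed | k = 1: reported / dosed |
|---|---|---|---|
| 0 | 10/10 = 1.00 | 40.0% / 40.0% | 10.0% / 10.0% |
| 1 | 9/10 = 0.90 | 40.0% / 44.4% | 10.0% / 11.1% |
| 2 | 8/10 = 0.80 | 40.0% / 50.0% | 10.0% / 12.5% |

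**Step 4: run-in events.**
- Protocol 10.2 records adverse events from consent, so events from C1/D-14 to C1/D-1 are collected. Water is taken on 7 of those 14 days.
- Every table by system organ class and preferred term in SAP 6.11.1.1 is a TEAE table, so none of these events enters one. SAP 6.1 puts them in subject listings.
- One possible exception is the overall summary row for CTCAE grade 3 or higher events. It is worded for AEs rather than TEAEs and, read literally, could pick up a severe run-in event.

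**The case against.** The strongest reply is that the dilution may never occur. Randomization and first dose are one day apart within a single in-house stay, and the check-in exclusions are applied at that stay. That stands: m may well be 0, and the effect is then nil. Nor is there a predictable bias between arms, since a never-dosed subject could fall in any group. SAP 6.2 reports randomized and treated counts separately, so such a subject would be visible, although the TEAE percentages would still be computed on the wrong base.

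It can also be said that SAP 6.3 foresees the two sets differing and that SAP section 4 has membership settled in a memo before database lock. This helps less. The sets coincide by schedule rather than by definition, so a difference would need a departure from the schedule. The memo must also apply the definitions as written, so it cannot repair them.

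Excluding non-randomized water takers is explicit and sensible, because they have no treatment group. Only its absence from SAP section 7 is open to criticism.

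A reader might infer that the safety of deuterated water goes unsummarized. The documents do not support that. The second water period (C4/D1 to C4/D7) falls inside the TEAE window and is tabulated. Run-in vital signs are taken at C1/D-14, D-11 and D-7, and vital signs are summarized by visit. Run-in events of randomized subjects are listed. Water is a labelling agent given on the same schedule to everyone, and the primary safety objective concerns FT-4101.

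A reader might also infer that dizziness is expected under the planned intake. Protocol 7.3.3.2 ties it to intake faster than this study plans.

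**Conclusion.** The mismatch between numerator and denominator is real and follows from the written definitions and the visit schedule. Its numerical effect is conditional: the reported TEAE rate is 1.00, 0.90 or 0.80 of the rate in dosed subjects for 0, 1 or 2 never-dosed subjects in a group of 10. Those counts are assumptions. The result also rests on subjects following the schedule and on study drug meaning IP, which SAP 6.1.5.1 supports.

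It would go too far to conclude that the primary safety rates will be diluted, or that a treatment comparison is biased in a known direction. The documents show only that the definition permits dilution. The missing run-in table and the missing section 7 entry are secondary reporting points. Overall this is a minor but worthwhile correction, because it concerns a primary endpoint and costs almost nothing.

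**What to change.** - In SAP 4.2, define the Safety set used for TEAE and other post-dose safety summaries as randomized subjects with at least one dose of IP. The conditional baseline table in SAP 6.3 then has a purpose, since the set differs from the Randomized set whenever someone is randomized but not dosed.
- In SAP section 7, list this change and the existing exclusion of non-randomized water takers as departures from protocol 12.2.1.
- Optionally, add a small table of adverse events with onset from first deuterated water to first IP dose. It would cover randomized subjects, plus non-randomized water takers where their events were recorded.

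The first two items are wording changes and need no new data. They should be settled before the analysis-set memo is finalized. The optional table is one extra output for randomized subjects. For non-randomized water takers it may be incomplete: protocol 11.1 limits screen-failure data to consent date, demographics and eligibility, and the documents do not say whether a run-in failure counts as a screen failure.
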